8. DATA COLLECTION AND MEASUREMENTS

Data Collection Assessment Periods

Eligibility, baseline and follow-up data will be collected by phone and at in-person visits in the home or in the clinic site waiting room. Intervention process data will be collected separately. In-person data collection visits will be conducted in the waiting rooms of the participating clinics. The following contacts describe the primary data collection points for participant level data.

Prescreen Contacts: During the initial waiting room contact, research staff will provide information about the trial and will collect additional data on eligibility. Those who remain interested and eligible will be consented to participate in the screening phase and will begin to complete screening visit measures. Most patients will complete screening and enrollment activities in this initial visit, some will finish the self-report data assessment but many will be

Patterned after protocol published online in association with Appel et al. (2011)¹⁵

called up for their appointment and therefore will have to leave off completion of the self-report data assessment at a later time. The study participant will be scheduled for an in-person screening visit and will be provided a number to call if interested in asking additional questions.

Screening Visit: Interested persons who are unable to complete screening and enrollment procedures during their first contact will be scheduled at their TCC clinic site from which they were recruited, where their blood pressure, waist circumference, height and weight will be measured. If these measures indicate continued eligibility then the participant will be provided more detail about the trial. Written informed consent to participate in the full trial will be obtained. After consent has been signed, the patient will be randomized and questionnaire data be collected.

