Randomization procedure. If all screening and baseline measures indicate that the patient remains eligible, a programmed application in REDCap generates a random assignment to experimental condition for the patient at the end of the screening assessment. The lifestyle change coaches can look up in REDCap's database the study participants assigned to their condition. The coach will then call the patient and arrange for the first coaching session, if appropriate. The research assistants will be kept ignorant of the patient's assignment to experimental condition, to reduce the chance for bias. Of necessity, the lifestyle change coaches will be aware of the patient's experimental assignment but will be instructed to follow the protocol carefully, so as not to introduce any personal bias.

The REDCap data entry system has also been programmed to generate a randomly determined assignment to condition, if the would-be participant met all inclusion criteria and reported no exclusion criteria. Hence, at the completion of the screening visit the study participant will be informed about the experimental condition that he/she had been assigned to and the name and contact number of his/her lifestyle coach. More information about the randomization process is provided below.

Follow-Up (FU) Visits: Participants will be asked to attend in-person follow-up visits at 6 and 12 months after randomization. Most of these data will be collected in-person at the clinic but the FFQ may be administered over the phone, depending on the time constraints of the study participant. The target windows used to schedule participants will coincide with a one month period around the 6 and 12 months follow-up visits. During follow-ups, we will also ask patients to evaluate the trial, including their perceptions of the acceptability and usefulness of the intervention and its components (MyPlate or Calorie Counting).

Measurement intervals.

Most measures will be assessed at baseline, at 6 months and 12 months follow-up. The Block Food Frequency Questionnaires will be administered only at baseline and 12-months follow-up, not at 6-months follow-up, to minimize the burden on study participants. Questionnaires were administered in the order described below in Table 4.

Table 4: Data Collection Items and Schedule by Contact

	Screening	Baseline	F-up-6	F-up-12
Eligibility/Interest	X			
Informed Consent	X	X		
Weight (self-reported)	X			
Height (self-reported)	X			
Weight (measured)		X	X	X

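### No provision requires the baseline self-reports to be finished before the participant learns the arm, and many participants may finish them later, so some baseline hunger ratings could be given knowing the arm

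*Combined protocol and SAP*

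**What the plan says.** Section 8 (Data Collection and Measurements) describes two routes into the trial.

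Under Prescreen Contacts, at the first waiting-room contact: "Most patients will complete screening and enrollment activities in this initial visit, some will finish the self-report data assessment but many will be" called to their appointment and so "will have to leave off completion of the self-report data assessment at a later time". No limit is put on the delay. The next sentence adds: "The study participant will be scheduled for an in-person screening visit". The opening of the section also allows telephone and home collection: "Eligibility, baseline and follow-up data will be collected by phone and at in-person visits in the home or in the clinic site waiting room".

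Under Screening Visit, for people who could not complete screening and enrollment at first contact, blood pressure, waist, height and weight are measured, eligibility is confirmed and consent is taken. Then: "After consent has been signed, the patient will be randomized and questionnaire data be collected".

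Under Randomization procedure: "If all screening and baseline measures indicate that the patient remains eligible, a programmed application in REDCap generates a random assignment". The same subsection then describes the programmed REDCap check as meeting the inclusion criteria and reporting no exclusion criteria. It goes on to say that "at the completion of the screening visit the study participant will be informed about the experimental condition that he/she had been assigned to". Of the coach it says: "The coach will then call the patient and arrange for the first coaching session, if appropriate". Section 10 repeats the eligibility condition and states that participants are not masked.

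Table 4 lists the hunger, fullness and satisfaction ratings, the SF-12 and the self-efficacy scales at baseline, 6 and 12 months. Its questionnaire rows are in order of administration: the SF-12 is third, hunger seventh and the WEL-SF eleventh.

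**The concern.** Everyday hunger is the primary patient-centered outcome. It is the participant's own rating in a trial where participants know their arm and where the stated hypothesis favors MyPlate. Keeping research assistants masked does not protect such a rating. Baseline is the one occasion on which an open-label trial can still collect it free of knowledge of the arm.

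The first-contact route puts that at risk. A patient may be found eligible, enrolled and told the arm, yet be called to the examination room before reaching the seventh questionnaire. The rest would then be answered with the arm known, possibly after the coach's first call. If late ratings shift differently in the two arms, a difference arises at baseline that randomization did not produce, and an analysis that uses baseline hunger carries it into the treatment effect. The SF-12 and the self-efficacy scales are open to the same problem.

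**Working it through.** **Sequence, provision by provision (sections 8 and 10)**

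1. What triggers assignment? Measures that show the patient remains eligible; the REDCap check is the inclusion and exclusion criteria. Hunger, the SF-12 and self-efficacy are not eligibility items. The mention of all screening and baseline measures could be read to include the questionnaires. On that reading it conflicts with the screening-visit order of randomization, then questionnaire. Read as eligibility checks, the provisions agree. Neither reading yields a rule that self-reports be complete before disclosure.
2. What triggers disclosure? Completion of the screening visit, not completion of the questionnaire.
3. Who may finish late? Those called away at first contact, described as many, in a passage that has most patients completing enrollment at that contact.
4. What does the order in Table 4 add? Randomization appears above the questionnaires, but only the questionnaire rows are said to be ordered. That row position and the screening-visit sentence concern randomization. Only knowledge of the arm can color a self-report, so neither shows exposure by itself.
5. What is unaffected? Baseline weight, which is measured before consent and randomization on the screening-visit route.

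**When it would reach the hunger result**

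Let f be the share of baseline ratings given knowing the arm, s the between-arm shift in those ratings, and r the baseline-to-12-month correlation. The bias is f × s for a change score, about r × f × s with baseline as a covariate, and zero if 12-month scores alone are compared. The documents give neither f nor s, nor the sign of s, so no figure can be put on it.

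Nor do they fix the model. Section 14 speaks of a longitudinal analysis of change using a linear mixed model. Section 13 words the hunger test as the 12-month report. Section 8 defines weight, but not hunger, as a baseline-to-12-month difference.

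**The plan's hunger sample size**

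Inputs from section 13: difference 53.5 − 46.7 = 6.8 mm, SD 13.2 mm, two-sided alpha 0.025, power 0.80.

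- Total N = 4 × (2.2414 + 0.8416)² × (13.2/6.8)² = 143.3, or 72 per arm and 144 in total, as stated.
- If the stated rho of .85 were used as a baseline-to-12-month correlation in a covariance analysis, the total would be 143.3 × (1 − 0.85²) = 39.8, about 40. The 144 therefore takes no credit for baseline hunger.

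**Precision of the remedies**

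Assumptions: 209 analysed (261 less 20%; section 13 gives 20% for 6 months and no 12-month figure), so 104.5 per arm; SD 13.2 mm for a single 12-month rating; r = 0.85 or 0.5 as an assumed baseline-to-12-month correlation, since the plan does not define its rho that way.

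With a share m of baselines set to missing, all participants kept and a common baseline mean:

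SE = 13.2 × √(2/104.5) / √[(1 − m)/(1 − r²) + m]

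| Baselines missing | SE, r = 0.85 | SE, r = 0.5 |
|---|---|---|
| none | 0.96 mm | 1.58 mm |
| one quarter | 1.06 mm | 1.63 mm |
| one half | 1.20 mm | 1.69 mm |
| all (12-month scores only) | 1.83 mm | 1.83 mm |

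Power without baseline: 6.8/1.826 − 2.2414 = 1.48, about 93%. With 183 analysed (30% loss) the SE is 1.95 mm and power about 89%. At 209 analysed, power stays at 80% or more up to an SD of 6.8/[3.083 × √(2/104.5)] = 15.9 mm.

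**The case against.** The strongest reply is that the sequence is sound when read as a whole. On the screening-visit route the questionnaire belongs to the visit and disclosure comes at its end, so ratings made there precede knowledge of the arm. Patients called away at first contact may be among those booked for a later screening visit, and so not yet assigned or told. Telephone use is named specifically only for the food frequency questionnaire at follow-up. The hunger item asks about the previous day, so a same-day answer describes a day before assignment. And section 13 words the hunger test as the 12-month report, with a sample size that takes no credit for baseline.

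Most of this stands. A reader might infer from the screening-visit sentence, or from the row order of Table 4, that baseline hunger is routinely rated with the arm known. The documents do not support that, because both concern randomization and not disclosure. The sentence on telephone and home collection likewise assigns no mode to the hunger rating.

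What the reply does not remove is the deferral provision. The later screening visit is described for people who could not complete screening and enrollment; someone who enrolled but left the questionnaire unfinished is not clearly covered. The delay is unlimited, so the previous day may fall after disclosure. Section 14 leaves open an analysis that uses baseline hunger.

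**Conclusion.** The gap is real and should be closed, as a possible and unquantified bias. It rests on two provisions taken together: many participants may finish the self-reports later, and disclosure is tied to the end of the screening visit with no condition that the self-reports be complete. Whether anyone was exposed, how many, and in which direction ratings would move cannot be learned from the documents. If few were exposed, the effect is negligible.

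A reader might also conclude that the hunger effect is biased by some share of the planned 6.8 mm, or that the weight result is compromised. Neither follows. Any such share would come from assumed inputs, and baseline weight is measured before randomization. The hunger result is touched only if baseline hunger enters the model. The precision and power figures depend on the assumed numbers analysed, the assumed correlation, and an SD that section 8 associates with repeated ratings over a year in another trial.

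**What to change.** Reconcile Prescreen Contacts, Screening Visit, Randomization procedure and Table 4 in section 8, and Randomization in section 10, to one sequence: the arm is not disclosed and the coach does not call until the baseline self-reports are complete. Randomization need not be delayed. The cost is a later first coach call for those who finish late. Requiring self-reports before randomization would also work, but would mean a second contact for some patients in a trial whose accrual was slow (section 4, footnote 1). State whether baseline hunger enters the primary model, and how.

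That footnote reports achieved enrollment, so for data already collected:

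- Where completion dates exist, report by arm how many baseline self-reports were completed after disclosure, not merely after randomization. Section 15 names a randomization date but no questionnaire completion time.
- Add a hunger sensitivity analysis that sets only those baselines to missing and keeps the participants, with baseline modelled as one of the repeated outcomes so that no one is dropped. This assumes that finishing late does not depend on arm, which is why the counts are needed by arm.
- If completion was not dated, say so and add a comparison of 12-month scores without baseline. It removes this problem only; the 12-month rating is itself given knowing the arm.

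The work is wording in a few places, one statement on the hunger model and one sensitivity analysis.

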Primary Patient Medical Outcome: Weight (kg) will be measured at each assessment in the clinic setting. Weight in light indoor clothes without shoes will be recorded by trained, certified staff using a high-quality digital scale (Tanita). Duplicate measurements will be made to ensure accuracy. Weight will be measured in pounds for ease of interpretation by the participants and subsequently converted to kilograms for data analysis. Scales will be calibrated weekly using standardized weights. The weight at screening/baseline will be used to determine eligibility ($27.0 \leq \text{BMI} \leq 40.4$). The difference between body weight obtained at screening/baseline and 12 months follow-up will be the primary patient medical outcome.

Secondary patient-centered outcomes include: weight control self-efficacy, patient autonomy, health-related quality of life, and patient satisfaction.

Weight control self-efficacy will be assessed using the 8-item short version ¹²⁷ of the 20-item Weight Efficacy Life-style Questionnaire (WEL), a measure judged reliable and valid in obese populations.^{128,129} The WEL-SF provides a total weight self-efficacy score based on the sum of the item scores (total range = 0– 80). Higher scores indicate greater self-efficacy. The WEL has demonstrated good internal consistency reliability in a general overweight patient population (Cronbach's coefficient alpha = 0.95 for men, 0.93 for women).^{129,130} The WEL-SF correlates $r = .968$ (shared variance = .937) with the WEL, despite the 60% reduction in the number of items.¹²⁷ Because of the high shared variance, the short version was chosen over the long version in order to minimize respondent burden.

Patterned after protocol published online in association with Appel et al. (2011)¹⁵

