13. STATISTICAL POWER AND SAMPLE SIZE ESTIMATION

Hypotheses for the Two-Group Randomized Control Trial Design: The aim is to conduct an RCT of the impact of CC versus MyP on patient-centered outcomes in up to eight community clinic sites in Long Beach. Participants will include: 150 patients randomly assigned to receive

Patterned after protocol published online in association with Appel et al. (2011)¹⁵

CC from trained health coaches, another 150 patients assigned to receive MyP from another group of trained health coaches over the course of 12 sessions in six months.

Intervention check: Does exposure to MyP versus CC lead to increased patient reports of fruit and vegetable intake in MyP? A preliminary check will be made to confirm that one of the defining features of the MyP approach, namely a doubling of F&V intake, was reflected in study participants' daily intake of F&V assessed at follow-up. If no difference were observed in F&V assessed at follow-up then the validity of the experimental contrast would be jeopardized. There could still be experimental effects, but the causal mechanisms would be unknown. Because numerous studies have succeeded in getting patients to double their intake of F&V for up to four years, a negative outcome of this intervention check is unlikely.²⁵

Question: Does exposure to MyP versus CC lead to decreased patient 12-months reports of daily hunger ratings/ daily meal satisfaction ratings/ daily fullness ratings in MyP during a time when patients were trying to lose excess weight (primary)? Will exposure to MyP versus CC lead to increased patient weight control self-efficacy, patient quality of life and patient satisfaction with her/his weight control program (primary)?

Question: Will exposure to MyP versus CC lead to increased weight loss/ reduced waist circumference equally for both conditions sustained for 12 months (secondary)?

Avoidance of bias. Covariates and effect modifiers. Standard demographic variables, including gender, age, ethnicity, marital status, and educational attainment will be included as covariates. Possible effect modifiers will also be included as covariates, including language preference (English / Spanish), last month food security, meal-skipping status, and daily physical activity level.

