Sample size. (3) Statistical power. We power this proposal for the two-group (MyP vs CC) randomized design, setting alpha at 0.025 in order to have an experiment wise type I error rate of 0.05 after testing two hypotheses. Test of hypothesis #1 is therefore a test of the effect of MyP versus CC on the 12 months report of freedom from hunger measure used in the trial most similar to the trial proposed here.¹⁸³ The intervention effect size reported by Ello-Martin and associates is Cohen's $d = .52$. (Cohen's Effect Size = $(53.5 - 46.7) / 13.2 = .52$). The total sample sized needed to detect this effect, given a two-tailed critical $P = .025$, minimum statistical power of .80, and $\rho = .85$ the total sample size needed is approximately $N = 144$. The test of the second hypothesis is a test of MyP versus CC on the body weight lost over 12 months. We have three sources to draw on for estimating effect size involving weight loss over 12 months. The first is Ello-Martin and associates, whose low-fat, high fruit and vegetables intervention²⁰ was similar to but not identical to the DASH diet + (sat. fat & sugar restriction) featured in the current proposal.¹⁶ Ello-Martin's DASH-similar + fat restricted diet yielded a 12-months weight loss of 7.9 kg (SE=0.9, n=35) whereas the fat restriction-only condition yielded a 12-months weight loss of 6.4 kg (SE = 0.9, n=36). The total sample size needed to detect a similar 12-months weight loss difference at $\alpha=0.025$, $\text{power}=0.80$, $\rho = .7$ is $N= 206$ ($n=103$ per group). In Appel's recent clinical trial¹⁵ the in-person DASH-like dietary intervention yielded a 5.4 kg (SE=0.7, n=124) weight loss relative to baseline at 12 months follow-up.¹⁵ The body weight lost in response to Wadden's DPP-like dietary intervention¹⁴ was 3.4 kg (SE=0.6, n = 112) at 12 months follow-up¹⁸⁴ By design the protocols followed by Appel et al. (2011) and by Wadden et al. (2011) were similar, so comparing means across these two studies is informative. The sample size needed to detect this difference at 12 months at $\alpha = 0.025$, $\text{power}=0.80$, $\rho = .7$ is $N = 270$ ($n = 135$ per group). Based on the best available sources in the literature for information about reasonable estimates of the effect size to be expected and given an expected attrition of 20% at 6 month follow-up, the baseline initial sample of 300 (N=300 for 2 groups) appears to provide ample statistical power for the two experimental comparison hypotheses

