14. ANALYSIS PLAN

General. After the data have been cleaned, we will examine the distribution and dispersion of data through descriptive numerical summaries and graphical tools such as scatter plots and box plots, probability plots, scatter matrix plots, co-plots, and trellis graphics to assess distributional assumptions and relationships among important variables. Before attempting a longitudinal analysis of the change in our outcomes using a linear mixed model, we will use profile plots, empirical summary plots and correlograms to guide us in the formulation of our model.¹⁸⁵ Some data will be subjected to scale transformation (e.g., logarithmic), as needed, to meet statistical assumptions. Box Cox or Yeo-Johnson transformations may also be used for this purpose.

Because missingness can potentially spoil or invalidate a study, we will spare no effort to minimize incomplete or missing data. All data will be carefully inspected to identify missing items, outliers, or other influential features. We will strive to form conclusions that are robust to different missing-data mechanisms,¹⁸⁶ and we will consult with colleagues in the Fielding School of Public Health Biostatistics Department regarding the use of incomplete-data analysis strategies that make effective use of available information.

Preliminary analyses will compare treatment groups on descriptive and clinical characteristics at baseline to ensure that randomization has succeeded. SAS (PC version 9.3) and Stata (Intercooled version 13) comprehensive database management and statistical packages will be used for descriptive calculations, group comparisons, and conditional regression modeling.

Experimental contrasts will be examined *a priori* using Stata's mixed effects modeling procedures, with standard errors corrected for the effects of clustered data.¹⁸⁷ It is known that even with randomized designs, covariate imbalance between treatment groups can exist and threaten the integrity of the design.¹⁸⁸ Because the potential bias may result in misleading conclusions, we will perform a thorough examination for covariate imbalance. Specifically, we will examine the distributions of all important variables at baseline and at the major endpoint (12 months follow-up), and also at intermediate points if the covariate is time-varying. Formal statistical methods for testing selection bias (systematic baseline imbalances) based on response data will be followed.^{188,189}

Missing and incomplete data

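### The plan never says how an outcome's own baseline value enters its model; if weight is analysed as raw change, baseline adjustment would cut the variance by about 15% at the plan's own correlation

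*Combined protocol and SAP*

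**What the plan says.** Four parts of the combined protocol and SAP bear on this.

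- **Weight endpoint (Section 8, Primary Patient Medical Outcome).** "The difference between body weight obtained at screening/baseline and 12 months follow-up will be the primary patient medical outcome". The Censoring text in Section 14 likewise bases the primary analysis on weight-change data.
- **Hunger endpoint (Section 13, Sample size).** Hypothesis 1 concerns "the effect of MyP versus CC on the 12 months report of freedom from hunger measure".
- **Covariates (Section 13, Avoidance of bias).** "Standard demographic variables, including gender, age, ethnicity, marital status, and educational attainment will be included as covariates". Possible effect modifiers are then added: language preference, food security, meal-skipping and physical activity. No baseline outcome value is named.
- **Model (Section 14, General).** The plan is a "longitudinal analysis of the change in our outcomes using a linear mixed model", with experimental contrasts from mixed-effects procedures. It does not say whether baseline is a response, a covariate or a mean common to both arms.

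Table 4 schedules weight and hunger at baseline, 6 and 12 months. Every sample-size statement in Section 13 quotes a rho: .85 for hunger and .7 for weight.

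**The concern.** In a randomized comparison of a continuous outcome, adjusting for its baseline value is, apart from the degree of freedom it uses, at least as precise as analysing the 12-month value alone or the change score. The baseline data are already being collected. An analysis that follows the endpoint definitions and the covariate list literally would not use them as a covariate.

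The sizing text refers to a within-person correlation, but the analysis text never says how that correlation is to be exploited. Section 14 also plans a thorough look for covariate imbalance without stating what adjustment follows. With the role of baseline left open, it could be settled after the data have been seen. At stake is precision, mainly for weight, the weaker of the two powered hypotheses.

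**Working it through.** **Inputs (Section 13 unless noted).** Two-sided alpha is 0.025 per hypothesis ("setting alpha at 0.025 in order to have an experiment wise type I error rate of 0.05") and power is .80. For hunger, the difference is 53.5 − 46.7 = 6.8 and the SD 13.2. For weight, source 1 is a year-long trial of two diets: 7.9 kg (SE 0.9, n=35) against 6.4 kg (SE 0.9, n=36). Source 2 compares a DASH-like arm with a DPP-like arm across two trials: 5.4 kg (SE 0.7, n=124) against 3.4 kg (SE 0.6, n=112). Attrition is 20%, stated for 6 months and used here for 12. Enrolment is 300, later 261 (Section 4). Rho is read as the baseline to 12-month correlation.

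**Formula.** n per arm = 2(z₁ + z₂)² × f × (SD/difference)², with z₁ = 2.2414, z₂ = 0.8416 and (z₁ + z₂)² = 9.505. With equal variances at the two times, f is 1 for the 12-month value alone, 2(1 − rho) for change and 1 − rho² for ANCOVA. The ratio of ANCOVA to change is (1 + rho)/2.

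**Reproducing the plan's figures**

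- Hunger, f = 1: 2 × 9.505 × (13.2/6.8)² = 71.6, so 72 per arm and N = 144. This is the stated figure, and it makes no use of rho = .85. With f = 0.30 (change) N = 44; with f = 0.2775 (ANCOVA) N = 40.
- Weight, source 1: the SDs of change are 0.9√35 = 5.32 and 0.9√36 = 5.40, pooled 5.36, and 1.5/5.36 = 0.28. At two-sided 0.025, N = 486 with no rho, 292 with f = 0.6 and 248 with f = 0.51. The stated 206 appears with f = 0.51 only at two-sided 0.05.
- Weight, source 2: the SDs are 0.7√124 = 7.79 and 0.6√112 = 6.35, pooled 7.15, and 2.0/7.15 = 0.28. N is again 486, 292 and 248. The stated 270 does not follow from the stated inputs with the pooled SD.

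So the sizing text does not settle which analysis is intended: 144 matches an unadjusted 12-month comparison, while 206 matches an ANCOVA factor at a different alpha.

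**Variance saved by ANCOVA**

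| rho | against change | against 12-month value alone |
|---|---|---|
| .7 (weight) | 1 − 0.85 = 15% | 1 − 0.51 = 49% |
| .85 (hunger) | 1 − 0.925 = 7.5% | 1 − 0.2775 = 72% |

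**Power for weight.** Take the cited SEs as SEs of change, so the SD already reflects the correlation, and multiply its variance by 0.85 for ANCOVA. Evaluable numbers are 300 × 0.8 = 240 and 261 × 0.8 = 208.8, taken as 209. Power = Φ(0.28 × √(N/4) / √f − 2.2414), here with f = 1 or 0.85.

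| Evaluable | change | ANCOVA |
|---|---|---|
| 209 | 41% | 48% |
| 240 | 47% | 54% |

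The N for 80% power would fall from 486 to about 414.

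**Power for hunger.** For the 12-month value alone, power is 93% at 209 and 96% at 240.

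**Sensitivity of the 15%.** Suppose the baseline SD is 0.9 of the 12-month SD (an assumption; the BMI limits could narrow the baseline spread). At rho .7 the change variance is then 1 + 0.81 − 2(.7)(.9) = 0.55 against 0.51, a saving of 7%. A ratio above 1 would raise it. The correlation matters too. With equal variances, an SD of change of 5.36 and rho of .7 imply a weight SD of 5.36/√0.6 = 6.9 kg (9.2 kg from source 2). The documents give no weight SD. For the same SD of change, a larger one means a higher rho and a smaller saving, such as 2.5% at .95.

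**The case against.** The strongest reply is that Section 14, not the endpoint definition, governs the analysis. Defining weight as a difference does not exclude a baseline covariate: change regressed on arm and baseline gives the same treatment effect as ANCOVA on the 12-month value. A mixed model with baseline as a response and a common baseline mean is about as precise as ANCOVA. That stands. A reader might infer that the plan commits to an inefficient analysis, and the documents do not support it. The loss arises only if baseline means are unconstrained (with complete data the baseline to 12-month contrast then equals the change-score estimate) or if change or the 12-month value is compared without its baseline. The plan does not say which applies.

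Three further replies have force.

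- A reader might expect much larger gains over a change score, on the view that a single hunger rating correlates weakly over a year. The only hunger correlation in the documents is .85, and Section 14 describes the longitudinal correlation as high.
- A reader might infer that the hunger test is in danger. On the plan's inputs it is not.
- Section 14 does promise an examination of baseline imbalance, and a change score does subtract baseline. Imbalance is therefore not ignored, though no adjustment rule is given.

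It could also be said that the covariate list is illustrative. But its examples are of demographics and effect modifiers; an outcome's own baseline value is not presented as either.

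**Conclusion.** The point holds as an unspecified role for baseline, with a conditional loss of precision. If weight is analysed as change without its baseline, ANCOVA would lower the variance by 15% at rho .7, worth about 7 percentage points of power at 209 or 240 evaluable. For hunger, the saving is 7.5% against change, or 72% against the unadjusted 12-month value, on a test that already has over 90% power.

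These sizes assume equal variances at the two times, rho read as the baseline to 12-month correlation, the cited SEs read as SEs of change, and 20% loss by 12 months. Adjustment does not by itself bring weight to 80% power on that reading. The point does not extend to satisfaction with the weight loss program, which Table 4 does not measure at baseline.

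**What to change.** 1. State in Section 14 that each outcome with a baseline measurement is analysed either with that value as a covariate (ANCOVA on the 12-month value or on change) or in a mixed model with arm means constrained equal at baseline. Name one approach as primary for weight and hunger before unblinded data are seen. Exclude program satisfaction.
2. Redo the weight sample-size statement on the same basis, saying whether the cited SEs are of change and at which alpha rho is applied.
3. Reconcile Section 8. Under Screening Visit, questionnaire data follow randomization. Under Randomization procedure, assignment is generated once screening and baseline measures are complete, and the participant is told at the end of that visit. Prescreen Contacts allows self-report to be finished later. Require baseline questionnaires, including hunger, before assignment is disclosed; flag any completed afterwards and examine them in a sensitivity analysis. Under Screening Visit, weight is measured before consent and randomization, so it is not affected.

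The cost is about one degree of freedom per model and a few sentences in the SAP. Item 3 may also need a small change in visit order; no new measurement is required.
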